### **Analysis of Demographics and Baseline Characteristics**

Demographics and baseline characteristics will include age, gender, race, comorbidities, baseline vital signs and laboratories. Descriptive statistics, including mean and standard deviation, median, intra-quartile ranges, minimum and maximum, and the number and percent of subjects in specified categories will be used to summarize the demographic and baseline variables for the two study arms. These will be compared between groups using independent two-sample test or Wilcoxon rank-sum test, as appropriate, for continuous variables and Chi-square test for categorical variables. Fisher's exact test will be used if  $\geq 20\%$  of the cells have expected cell count  $< 5$ . All statistical analyses will be done using SAS version 9.4 statistical software (SAS Institute Inc., Cary, NC).

## Patient Disposition

Disposition tables including patients signed informed consent, randomized (safety analysis set, full analysis set, per protocol set, pharmacokinetics analysis set), drop out with reasons will be prepared.

The number of subjects will be tabulated overall for the following sets: safety population, subjects who completed study by period, and subjects who prematurely discontinued for study drug, for each treatment group and overall, as appropriate. Additionally, the number and percentage of subjects who discontinued study drug will be summarized by reason for each treatment group and overall. All reasons and primary reasons for discontinuation of study drug will be summarized as recorded on the eCRF by the following categories:

- Adverse event (AE)
- Protocol violation
- Lost to follow-up
- Withdrawn by subject
- Lack of efficacy

Subjects may have more than one reason for discontinuing study drug, but they will be counted once for the total number of discontinuations. Subjects have only one primary reason for discontinuing study drug or discontinuing from the study.

## Primary Endpoints

### Primary Clinical Endpoint

- The primary clinical efficacy variable is time to intubation event in hours from the start of study infusion.

### Statistical Method for the Primary Clinical Efficacy Endpoint

Kaplan-Meier estimates of the survival functions will be graphically displayed for each treatment group. Kaplan-Meier quartiles (25th percentile and median) with two-sided 95% confidence intervals will be calculated if applicable. In addition, time to intubation will be summarized via displaying number of

subjects at risk, the percent of subjects that are censored, and Kaplan-Meier event rates with two-sided 95% confidence intervals.

A log-rank test stratified by the randomization stratification factor (age group) will be used to compare the time to intubation of the two treatment groups. The hazard ratio of IV Citrulline compared with placebo and its corresponding two-sided 95% confidence interval will be estimated using a Cox proportional hazards (PH) model with treatment groups as the independent variable and stratified by the age group.

### **Analysis of Covariates for Primary Clinical Endpoint**

The covariates in Table 3 will be analyzed for the primary clinical outcome (time to intubation) in the ITT population. The 95% two-sided confidence interval of the hazard ratio of IV Citrulline compared with placebo, adjusted for each covariate separately from the Cox PH model will be obtained. Due to small sample size of this Phase II trial, the Cox PH model adjusted for all covariates simultaneously will not be performed. Additionally, each covariate will be re-examined and appropriately re-categorized if model convergence (i.e. quasi-separation) occurs due to sample size.

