## STUDY ENDPOINTS AND COVARIATES

**Table 1: Primary and Secondary Efficacy Endpoints**

Primary Clinical Efficacy Variables:	The primary clinical efficacy variable is time to intubation event in hours from the start of study infusion.
Secondary Clinical Efficacy Variables:	

1. All-cause hospital mortality

2. The requirement for intubation and invasive mechanical ventilation

3. Length of non-invasive mechanical ventilation in hours

4. Length of oxygen therapy in hours

5. Length of ICU stay in hours

6. Length of hospital stay in hours

7. Difference in proportion of patients intubated

8. Difference in proportion of patients intubated and on MV

Secondary Biochemical Efficacy Variables:	

1. Plasma levels of citrulline at 2 hours, 12 hours, and study days 2, 4, 8, 10.

2. Plasma levels of arginine at 2 hours, 12 hours, and study days 2, 4, 8, 10.

3. Plasma NOx levels at 2 hours, 12 hours, and study days 2, 4, 8, 10.

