**Table 2: Secondary Safety Endpoints**

Safety Variables:	

1. Primary safety variable is hemodynamic status, specifically worst vasopressor dependency index through day 10.

2. Incidence of reported adverse events.

Safety Evaluations:	
In addition to vasopressor dependency index, the following laboratory values will be used for safety assessment at baseline and daily through study day 4 when available.
 

1. Complete blood count with platelets

2. Basic Metabolic profile, including renal function

3. Liver function tests, including SGOT, SGPT, total bilirubin, and alkaline phosphatase

 
Adverse events will be recorded prospectively, including incidences of hypotension, hepatitis (i.e., the elevation of liver enzymes), and injection site reactions.

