**Table 3: Covariates**

Independent Variables:	Age is likely to be an independent covariate and the intention is to assess its contribution in two age groups (younger and older) as per protocol.
Dependent Variables:	The outcome variable of interest being reduction in morbidity and mortality outcomes. A fuller list is as per the secondary endpoints above.
Continuous variable:	The study involves markers of respiratory function such as P/F ratios and hemodynamic markers such as VDI that are considered continuous variables and are expected to change with study treatment.

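### The adjusted hazard ratios for time to intubation draw on a covariate table that gives P/F and VDI no measurement time and includes an outcome row; adjusters should be limited to pre-infusion values

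*SAP*

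**What the plan says.** The primary analysis of time to intubation (SAP, Statistical Method for the Primary Clinical Efficacy Endpoint) is a log-rank test stratified by age group, with a Cox model "with treatment groups as the independent variable and stratified by the age group".

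The next section, Analysis of Covariates for Primary Clinical Endpoint, adds: "The covariates in Table 3 will be analyzed for the primary clinical outcome (time to intubation) in the ITT population". It asks for the treatment hazard ratio and 95% interval from Cox models that each adjust for one covariate, and rules out a joint model because the trial is small. It names no covariate and no measurement time.

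Table 3, which is titled Covariates, has three rows:

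- **Independent Variables.** "Age is likely to be an independent covariate and the intention is to assess its contribution in two age groups".
- **Dependent Variables.** Morbidity and mortality outcomes, then: "A fuller list is as per the secondary endpoints above".
- **Continuous variable.** P/F ratios and VDI are given as examples of markers that "are expected to change with study treatment". No time point is given.

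The VDI variable in SAP Table 2 is an on-study outcome: "Primary safety variable is hemodynamic status, specifically worst vasopressor dependency index through day 10".

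**The concern.** A covariate-adjusted hazard ratio estimates the treatment effect only if the covariate is fixed before treatment can act on it. Age group meets that condition. P/F and VDI meet it only if they are measured before the infusion starts, which the plan does not require. If a programmer takes the first scheduled on-study oxygenation value, or the VDI variable defined in Table 2, the model holds constant something the drug may already have changed. Its hazard ratio then describes whatever part of the effect does not pass through that marker.

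The section's only safeguard would not catch this: "each covariate will be re-examined and appropriately re-categorized if model convergence (i.e. quasi-separation) occurs due to sample size". It responds to a model that fails to converge, and a Cox model containing a mediator usually converges without trouble.

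At stake is a set of supplementary intervals likely to be read alongside the primary hazard ratio. They could make a real effect look absent or make it look larger than it is.

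**Working it through.** **1. Where timing is stated, and where it is not**

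| Place | Marker | Timing as a covariate |
|---|---|---|
| Protocol Study Summary, statistical considerations | S/F or P/F | baseline (for the lung-injury ANCOVA) |
| Protocol 10.5; SAP, Hemodynamic status | VDI | baseline (for the worst-VDI ANCOVA) |
| Protocol 7.2.1 | MAP, vasopressor dose | within 15 minutes before infusion |
| SAP Table 3 and covariate section | P/F, VDI | none |

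The first two rows concern other analyses, and nothing carries them over to the Cox models for intubation.

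**2. What a pre-infusion value would rest on**

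- *Oxygenation.* Appendix A first marks S/F on Day 1, without the hour-0 and pre-dose footnotes carried by MAP and vasopressor dose. The Study Summary nevertheless lists a day 0 value and a baseline value. The two do not agree. Appendix B makes blood gases optional, so P/F will not exist for everyone.
- *VDI.* Patients enter on the floor, not intubated (Protocol 6.2), and VDI is derived once a patient becomes critically ill (SAP, Study Assessments). Pre-infusion VDI is therefore probably zero in nearly all patients (an assumption).

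**3. Age group**

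Age group is constant within each stratum of the primary Cox model, so an age-group term cancels from the partial likelihood and cannot be estimated. The age row adds nothing to the stratified model.

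**4. Direction and size for a post-infusion marker**

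The sample-size section supplies hazard ratio 0.46, a placebo time to intubation of 3 days and 60 patients. Its 81% power reproduces with 60 events: √60 × (1 − 0.46)/(1 + 0.46) − 1.96 = 0.905, and Φ(0.905) = 81.7%. Nothing below depends on that power figure.

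Let m be the share of the log hazard ratio that runs through the marker. The documents give no value for m. Adjusting for the marker leaves (1 − m) × ln 0.46, so

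HR adjusted = 0.46^(1 − m).

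The simulated columns use 20,000 patients, 10 days of follow-up, a placebo median of 3 days, an assumed log hazard ratio of −0.7 per SD of the later marker, and correlation 0.6 with its pre-infusion value.

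| m | Formula | Adjusted, later value | Adjusted, pre-infusion value | Treatment only |
|---|---|---|---|---|
| 0 | 0.46 | 0.472 | 0.523 | 0.549 |
| 25% | 0.56 | 0.572 | 0.515 | 0.536 |
| 50% | 0.68 | 0.691 | 0.515 | 0.536 |
| 75% | 0.82 | 0.810 | 0.506 | 0.526 |
| 100% | 1.00 | 0.990 | 0.497 | 0.528 |

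If the drug worsens the marker, m is negative and the formula gives 0.46^1.25 = 0.38 at −25% and 0.46^1.5 = 0.31 at −50%. A second simulation (60 patients, Cox model stratified by age, log hazard ratio −0.9 or −0.4 per unit of marker) gave 0.35–0.37 and 0.30–0.31.

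The treatment-only value exceeds 0.46 even at m = 0 because the hazard ratio is non-collapsible. What matters is that the pre-infusion column barely changes with m, while the later-value column follows m.

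With 60 patients per trial (600 runs), the chance that the 95% interval lies below 1 is:

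| m | Treatment only | Pre-infusion value | Later value |
|---|---|---|---|
| 50% | 53.7% | 58.5% | 24.5% |
| 100% | 50.5% | 56.5% | 2.7% |

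For a VDI-like marker, zero in 37–90% of patients and more often positive after intubation, the hazard ratio moved only from 0.45–0.47 to 0.45–0.55.

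**The case against.** **Baseline was intended.** This is the best defence. Wherever else the documents name these markers as covariates, they use baseline values. The phrase about change with treatment describes the markers and does not schedule a post-infusion adjuster. So a reader who infers that the SAP has chosen post-infusion values goes further than the text. What stands is that the plan permits such a value and does not exclude it.

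**The outcome row is only a label.** A reader might infer that the SAP plans to adjust time to intubation for intubation itself, because the row refers to the secondary endpoints and these include "The requirement for intubation and invasive mechanical ventilation". Read literally, that model would break down: the event indicator has no finite coefficient. But the row is headed Dependent Variables and most naturally names the outcome side of the model. The section's plural wording does not bring it in, since age, P/F and VDI already make three covariates. The row is misplaced in a covariate table, and no effect size should be attached to it.

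**The mediation figures return their own input.** Largely true: the simulated values follow 0.46^(1 − m) because m was built in. They illustrate direction and do not forecast this trial. With a strong marker and m = 25%, the second simulation gave an adjusted value of 0.56 against a treatment-only 0.54–0.58, so no shift would be visible.

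**The analysis is supplementary.** This is also true, and it limits the weight of the point.

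**Conclusion.** The point holds as a specification gap in a supplementary analysis. As written, Table 3 and the covariate section allow an adjusted hazard ratio that conditions on a marker the drug may already have moved. Such a ratio would not estimate the treatment effect, and its error could go either way. The size depends on a mediation share that the documents do not give. For VDI the distortion may be small.

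A reader might infer that the primary result is compromised. It is not: the stratified log-rank test and its hazard ratio use none of these covariates, and the covariate section attaches no decision to its intervals. The correction is worth making because it is specific and nearly free.

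**What to change.** In SAP Table 3 and the covariate section:

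1. Delete the Dependent Variables row.
2. Restrict adjusters to values measured before the start of infusion, and state the time point.
3. Use one oxygenation scale for every patient. S/F is the practical choice because Appendix B makes blood gases optional. Take the last value before time zero and enter it in the Cox model stratified by age group.
4. Do not add age group as a term. If no pre-infusion S/F exists, the primary stratified hazard ratio stands alone.
5. Omit VDI, or use only the pre-infusion value from Protocol 7.2.1 and report how many patients exceed zero.
6. Reconcile the Study Summary (day 0 and baseline S/F or P/F) with Appendix A (S/F first marked on Day 1, no hour-0 footnote). A Day 1 value taken after time zero must not serve as baseline.

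The cost is SAP wording before database lock, with no new procedures and no change to sample size or the primary test. Someone must confirm that charted oxygen saturation and oxygen settings give a pre-infusion S/F, because the documents do not establish this.

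A separate, minor and free improvement: stratify the time-to-death log-rank test and Cox model by the randomization age group. The unstratified test is valid but slightly conservative if age predicts death. In simulation with 50% placebo deaths and an assumed age hazard ratio of 3, type I error was 3.7% unstratified against 4.8% stratified. Power at a treatment hazard ratio of 0.4 was 51.8% against 56.9%. Across the settings tried, the power gain ran from 0 to about 5 points.

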## **SECONDARY ENDPOINTS**

### **Secondary Clinical Endpoints**

- All-cause hospital mortality
- The requirement for intubation and invasive mechanical ventilation
- Difference in proportion of patients intubated
- Difference in proportion of patients intubated an on MV
- Length of ICU stay in hours
- Length of hospital stay in hours
- Length of oxygen therapy in hours
- Length of non-invasive mechanical ventilation in hours

### **Statistical Method for the Secondary Clinical Efficacy Endpoints**

#### ***All-cause Hospital Mortality***

All-cause, hospital mortality, defined by whether the patient was discharged from the hospital alive or deceased, will be analyzed via two statistical methods. The proportion of patients who have died by

hospital discharge will be analyzed using a Fisher's Exact Test. Additionally, time to death will also be analyzed using Kaplan-Meier estimates of the survival functions. A log-rank test will be used to compare time to death for the two treatment groups. The hazard ratio of IV Citrulline compared with placebo and its corresponding two-sided 95% confidence interval will be estimated using a Cox proportional hazards (PH) model with treatment groups as the independent variable.

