2.0 STUDY SUMMARY

Title: Prospective, Randomized, Double-Blind, Placebo-Controlled Phase II Trial of Intravenous L-Citrulline to Delay and Potentially Prevent the Need for Invasive Mechanical Ventilation for Acute Hypoxemic Respiratory Failure in Patients with COVID-19 (SARS-CoV2) Illness.

Objective: To evaluate safety and efficacy of a bolus loading dose and continuous intravenous infusion of L-Citrulline compared to placebo in patients hospitalized with COVID-19 infection (SARS-CoV-2).

Hypothesis: Intravenous L-citrulline administration will safely restore the homeostasis of nitric oxide synthase by increasing both plasma citrulline and arginine levels. We also reason that restoration of citrulline/arginine balance through citrulline administration will safely re-establish homeostasis of NOS, lower oxidative stress, and reduce inflammation, thereby delaying and potentially preventing the need for invasive mechanical ventilation in patients hospitalized with COVID-19 infection (SARS-CoV-2).

Study Design:	
Prospective, randomized, placebo-controlled, double-blind design.
 
 1. Enrollment: approximately 6-9 months 2. Plasma citrulline and arginine levels at day 4 will represent the primary biochemical variable. 3. Vasomotor stability, as measured using a vasopressor dependency index (VDI), through study day 10, will represent the primary safety variable. 4. The length of time from the initiation of the treatment to an intubation event for invasive mechanical ventilation measured in hours will represent the primary clinical outcome. 5. Patients will be followed until hospital discharge for mortality, ICU and hospital lengths of stay, and a requirement for invasive mechanical ventilation and non-invasive mechanical ventilation with high flow nasal cannula or BiPAP as additional clinical endpoints. A further comparison will be performed at D28 and D60 based on telephone follow up for those discharged earlier. 6. Patients will exit the study early (prior to 10 days) if they recover and no longer require oxygen therapy.

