5.0 STUDY DESIGN

5.1 Study Description

This is a randomized, double-blind, placebo-controlled, phase II study to evaluate the safety and efficacy of intravenous L-Citrulline in reducing the length of time from the start of study infusion to an intubation event in hospitalized acutely ill patients with an acute hypoxic respiratory illness due to COVID-19 infection (SARS-CoV2). Patient's age of 18 years old and less than 65 years old inclusive with COVID-19 infection (SARS-CoV2) will be included in the study.

Only subjects hospitalized at UAMS and requiring oxygen for an acute hypoxic respiratory illness due to COVID-19 (SARS-CoV2) will be included in this study. Study drug administration will occur exclusively in the hospital.

In addition, subjects will receive standard supportive care for acute hypoxic respiratory illness and failure.

Up to 66 participants ages 18 years to 65 years, inclusive, who meet all the inclusion criteria and none of the exclusion criteria will be randomized into the study over approximately 6-9 months.

The study consists of an initial Study Drug bolus followed by a continuous infusion for a maximum of 10 days. The safety and efficacy will be evaluated through hemodynamic monitoring, laboratory assessment, oxygenation status, and biomarker measurements through study day 10. Adverse events will be monitored through study day 10. Clinical outcomes, including all-cause mortality, ICU length of stay, and hospital length of stay will be assessed through hospital discharge with a telephone follow up at D28 and D60, if discharged earlier.

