7.2.3 Clinical Outcome Assessments

ICU length of stay will be calculated in days from time = 0 to the earlier of ICU discharge or death. Any re-admissions to the ICU during the hospital stay will add days to ICU length of stay. Hospital length of stay will be calculated in days from time = 0 until the earlier of hospital discharge or death. A follow up at D28 and D60 will further evaluate the stated clinical outcomes.

Concomitant medications and adverse events will continue to be monitored and recorded in the CRF for the duration of the participant's hospital stay.

See the Schedule of Procedures in Appendix A for further details.

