## INTRODUCTION

This document outlines the planned statistical analyses for data collected within the scope of Asklepion L-Citrulline protocol CIT-COVID19-002-01, entitled “Prospective, Randomized, Double-Blind, Placebo-Controlled Phase II Trial of Intravenous L-Citrulline to Delay and Potentially Prevent the Need for Invasive Mechanical Ventilation for Acute Hypoxemic Respiratory Failure in Patients with COVID-19 (SARS-CoV-2) Illness”. This statistical analysis plan (SAP) applies to the protocol v3.0, 11 June 2021. The purpose of this plan is to provide general, and in some instances, specific guidelines for which the various analyses will proceed. The primary analysis will include clinical efficacy, biochemical efficacy, and safety data up to the primary analysis data cut-off date.

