## **STUDY DESIGN**

This is a randomized, double-blind, placebo-controlled, phase II study to evaluate the safety and efficacy of intravenous L-Citrulline in reducing the length of time from the start of study infusion to an intubation event in hospitalized acutely ill patients with an acute hypoxic respiratory illness due to COVID-19 infection (SARS-CoV2). Patients age of 18 years old and less than 65 years old inclusive with COVID-19 infection (SARS-CoV2) will be included in the study.

Only subjects hospitalized at UAMS and requiring oxygen for an acute hypoxic respiratory illness due to COVID-19 (SARS-CoV2) will be included in this study. Study drug administration will occur exclusively in the hospital.

In addition, subjects will receive standard supportive care for acute hypoxic respiratory illness and failure.

Approximately 60 participants ages 18 years to 65 years, inclusive, who meet all the inclusion criteria and none of the exclusion criteria will be randomized into the study over approximately 6-9 months.

The study consists of an initial Study Drug bolus followed by a continuous infusion for a maximum of 10 days. The safety and efficacy will be evaluated through hemodynamic monitoring, laboratory assessment, oxygenation status, and biomarker measurements through study day 10. Adverse events will be monitored through study day 10. Clinical outcomes, including all-cause mortality, ICU length of stay, and hospital length of stay will be assessed through hospital discharge.

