### **Missing Data**

Although every effort will be made to minimize the amount of missing data, some level of missing data will be unavoidable for a variety of reasons. In general, data may be missing due to subject's early withdrawal from study. Patients discontinuing early from the study and reasons for withdrawal will be summarized by treatment group to see if any biases in the analyses may have been created by any differences between groups. For the study of time-to-event endpoints, patients completing the study and not experiencing an event of interest are considered censored to the event. The impact of missingness will be minimized in the analysis of the primary endpoint by performing the analysis using Kaplan-Meier estimate, where participants will be censored at their last assessed time point. The procedures outlined below describing what will be done when data are missing may be refined during the blind review of the data.

For this Phase II study, missing data imputation will only be done for the primary and secondary biochemical outcomes (i.e., plasma levels of citrulline, arginine, ornithine, and NOx). For the analysis of other safety and secondary endpoints, no imputation will be done for missing values.

Missing biochemical data, it will be minimized operationally as we are setting up significant oversight on sample logistics. Nonetheless, given the longitudinal nature of data collection for biochemical measures, there exist the possibility of data truncation due to patient death.

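### The SAP does not carry out the protocol's D28 and D60 comparison and gives time to death no horizon and no rule for patients discharged alive, so survivors would most naturally be censored at discharge

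*SAP*

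**What the plan says.** **Protocol.** Section 2.0 (Study Design, item 5) lists mortality among the outcomes followed to discharge and adds: "A further comparison will be performed at D28 and D60 based on telephone follow up for those discharged earlier". Section 7.2.3 says: "A follow up at D28 and D60 will further evaluate the stated clinical outcomes". Section 5.1 ends its sentence on clinical outcomes "with a telephone follow up at D28 and D60, if discharged earlier". Appendix A has columns for both days, and Appendix C gives each call a window of 2 days either side. Sections 7.1.4 and 10.6.1 define hospital mortality at discharge, and 10.6.1 adds a log-rank analysis of time to death.

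**SAP.** The Introduction states: "This statistical analysis plan (SAP) applies to the protocol v3.0, 11 June 2021". The Study Design section repeats the sentence from protocol 5.1 without its telephone clause: "Clinical outcomes, including all-cause mortality, ICU length of stay, and hospital length of stay will be assessed through hospital discharge". Its section on mortality says: "All-cause, hospital mortality, defined by whether the patient was discharged from the hospital alive or deceased, will be analyzed via two statistical methods". Fisher's exact test on the proportion dead by discharge comes first. Time to death by Kaplan-Meier, log-rank and Cox comes second: "A log-rank test will be used to compare time to death for the two treatment groups". That section gives no censoring time, no horizon and no treatment of discharge alive.

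The Missing Data section treats patients who finish the study without the event as censored. In describing the primary endpoint it adds the Kaplan-Meier rule "where participants will be censored at their last assessed time point". It also lists contact after discharge and ascertainment of vital status as steps against missing data, with no day and no analysis attached.

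**The concern.** Two things are at stake.

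First, the protocol commits to a comparison for which the SAP supplies no method. Followed as written, the SAP would not produce it, although patients are to be telephoned at both days.

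Second, time to death needs a follow-up period, and the only one the SAP gives for mortality ends at discharge. Kaplan-Meier and log-rank methods assume that a censored patient has the same future risk as those still under observation. Patients well enough to go home are very unlikely to share the risk of those still in hospital. Censoring them at discharge shrinks the risk set selectively and inflates the mortality curve. It also ties the between-arm comparison to how quickly each arm is discharged. Length of hospital stay is itself a secondary endpoint, so a difference in discharge timing is something the trial sets out to look for.

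**Working it through.** **1. The plan's own mortality figure.** SAP Sample Size: 60 patients (30 per arm), 50% vs 17%, two-sided 0.05, z-test with pooled variance, 80% power.

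- Pooled proportion: (0.50 + 0.17)/2 = 0.335.
- SE under the null: √(2 × 0.335 × 0.665/30) = 0.1219.
- SE under the alternative: √((0.50 × 0.50 + 0.17 × 0.83)/30) = 0.1142.
- Power: Φ((0.33 − 1.96 × 0.1219)/0.1142) = Φ(0.798) = 78.8%.

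This reproduces the stated 80% to within 2 points. It is the power of a comparison of proportions and does not carry over to a log-rank test that censors at discharge.

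**2. Assumptions for the rest.** The documents give no length of stay. I assume a mean stay of 7, 10 or 14 days, constant daily hazards of death and of discharge alive, and no deaths after discharge. Let p be the proportion who leave hospital by dying and L the mean stay, so the daily death hazard is p/L.

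- Kaplan-Meier mortality at day t with discharge censored: 1 − exp(−p·t/L).
- Proportion of all patients who have died by day t: p·(1 − exp(−t/L)).

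Example (p = 0.50, L = 14, t = 28): Kaplan-Meier 1 − exp(−1) = 63.2%; actually dead 0.50 × (1 − exp(−2)) = 43.2%.

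| p | L (days) | Day 28: KM | Day 28: dead | Day 60: KM | Day 60: dead |
|---|---|---|---|---|---|
| 50% | 7 | 86.5% | 49.1% | 98.6% | 50.0% |
| 50% | 10 | 75.3% | 47.0% | 95.0% | 49.9% |
| 50% | 14 | 63.2% | 43.2% | 88.3% | 49.3% |
| 17% | 7 | 49.3% | 16.7% | 76.7% | 17.0% |
| 17% | 10 | 37.9% | 16.0% | 63.9% | 17.0% |
| 17% | 14 | 28.8% | 14.7% | 51.7% | 16.8% |

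**3. Effect on the log-rank test.** Simulation under the same assumptions: 30 per arm, 2,000 trials per setting, horizon day 28 or day 60. The table gives rejection rates at two-sided 0.05 across the three stays and two horizons. Monte Carlo standard error is about 1 point.

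| Scenario | Censored at discharge | Vital status followed to the horizon |
|---|---|---|
| A. 50% vs 17%, same overall exit rate in both arms | 54–59% | 70–80% |
| B. 50% vs 17%, same daily death hazard, citrulline discharged faster | about 5% | 55–74% |
| C. 50% in both arms, citrulline stay 0.6 of placebo | 26–28%, on average toward harm | 6–9% |

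Scenario B is extreme: the citrulline mean stay is 0.17/0.50 = 0.34 of placebo's. In C both exits are speeded up equally, so deaths come earlier on citrulline, which explains why the fixed-horizon rate sits slightly above 5%. With discharge censored, the log-rank test compares the daily death hazard among patients still in hospital. That is a legitimate quantity, but it is not mortality.

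**The case against.** The strongest reply is that the SAP never says a patient discharged alive is censored at discharge for the death analysis. The rule on the last assessed time point is written for the primary endpoint. The general rule refers to completing the study, and under protocol v3.0 follow-up runs to days 28 and 60. On that reading a survivor reached by telephone is censored at the call. The SAP also intends contact after discharge and ascertainment of vital status. All of this stands: censoring at discharge is an inference from the SAP's Study Design, Missing Data and mortality sections taken together. What the text establishes is that the horizon and the censoring rule are missing.

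A reader might go further and infer three things the documents do not support.

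- *That deaths after discharge are lost altogether.* The SAP plans to learn vital status. It assigns that information to no analysis.
- *That the hospital mortality comparison is invalid.* The Fisher test of deaths by discharge is listed first and is not biased by this censoring. The discharge-based definition is also the protocol's own, so the SAP carries it over faithfully.
- *That identical mortality would be reported as grossly different.* Suppose each arm has 5 deaths among 30, and 20 patients in one arm and 24 in the other go home before any death. Kaplan-Meier mortality then reads 5/10 = 50% vs 5/6 = 83%. This requires every discharge to precede every death, which nothing in the documents suggests. With the same counts and exit times mixed at random (exponential, mean 10 days), the curves average about 30% vs 43%, the median log-rank p is about 0.7, and none of 2,000 runs rejects. Fisher would compare 5/30 with 5/30.

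Finally, Appendix A has no explicit vital-status row at D28 or D60. It lists hospital status, ICU status, medication review and adverse event review. Death can probably be inferred from these, but that should be confirmed.

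**Conclusion.** The omission is certain: the protocol promises a D28 and D60 comparison, and the SAP, which applies to the protocol version containing that promise, has none. It is also certain that time to death has no stated horizon and no rule for discharge alive. Censoring at discharge is the natural implementation but not a stated one.

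If it is implemented that way, a true 50% mortality reads as about 63–87% at day 28 and a true 17% as about 29–49%. Log-rank power for the SAP's own 50% vs 17% scenario is 54–59% instead of 70–80%, and differing discharge rates can hide a real difference or suggest a false one. These sizes rest on the assumed stays of 7 to 14 days, constant hazards and no deaths after discharge.

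Mortality is a secondary endpoint and the Fisher analysis is free of this bias, so the point should be corrected but does not threaten the primary result.

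**What to change.** Add to the protocol's hospital mortality endpoint; do not replace it.

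1. Keep Fisher's exact test of deaths by hospital discharge.
2. Under All-cause Hospital Mortality in the SAP, run Kaplan-Meier, log-rank and Cox for time to death to a fixed day-60 horizon, using hospital records and the D28 and D60 contacts. Censor survivors at day 60 or the date last known alive, not at discharge. If a curve of in-hospital death alone is also wanted, show cumulative incidence with discharge alive as a competing event.
3. Add day-28 and day-60 mortality comparisons with all randomised patients in the denominator. State how unknown vital status and calls made within the 2-day window are handled, and whether these tests join the Hochberg family for secondary outcomes.
4. Restore the D28 and D60 clause in the SAP's Study Design section so that it matches protocol 5.1.
5. Confirm that the D28 and D60 call form records vital status and date of death.

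The cost is SAP wording and a little programming before unblinding. The calls are already scheduled. The downside is some loss to telephone follow-up, which the report should show by arm.
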